1.0 Study Summary

Study Title	Influence of ultra-processed foods on reward processing and energy intake
Study Design	The study will utilize a randomized crossover design, with 2 weeks of controlled feeding followed by measuring changes in reward processing by fMRI. The overall objective of this study is to establish proof-of-concept for an altered reward processing in response to a UPF diet compared to a diet emphasizing MPF in the key developmental period of 18-25.
Primary Objective	To determine the influence of chronic UPF consumption on brain reward response to UPF.
Secondary Objective(s)	To determine the influence of chronic UPF consumption on ad libitum energy intake and food selection. Explore the influence of UPF consumption on executive function, specifically inhibitory control, cognitive flexibility, and working memory, as well as eating in the absence of hunger.
Study Population	Late adolescents/early adults aged 18-25
Sample Size	32
Research Intervention(s)/Investigational Agent(s)	Participants will be randomly assigned to a 2-week diet emphasizing either UPF (81% total energy) or un/minimally processed foods (0% UPF). Participants will be fed a eucaloric diet (50% carbohydrate, 35% fat, 15% protein) matched for dietary fiber, added sugars, saturated fat, mono- and poly-unsaturated fat, sodium, pre- and probiotics, micronutrients, and overall diet quality, for the duration of the study to avoid potential confounds of weight change and other dietary factors which may influence study outcomes. fMRI will be conducted 4 times where participants will be exposed to UPF milkshakes to assess reward processing. Ad libitum energy intake will be assessed.
Study Duration for Individual Participants	1-2 weeks of screening and baseline testing followed by 2, 14-day feeding periods; followed by 2 days of post-intervention testing and a 4 week washout period in between feeding conditions. The total estimated duration for participants is ~10-12 weeks.
Acronyms and Definitions	UPF: Ultra-processed food MPF: Minimally processed food EI: Energy intake EF: Executive function ED: Eating disorders PA: Physical activity LHS: Labeled Hedonic Scale HEI: Healthy Eating Index TFEQ: Three-Factor Eating Questionnaire mYFAS: modified Yale Food Addiction Scale

	LEC5-Life Events Checklist 5 BIA: Bioelectrical Impedance Analysis DD: Delay Discounting
--	--

2.0 Objectives

2.1 *Describe the purpose, specific aims, or objectives of this study:*

Aim 1: To determine the influence of chronic UPF consumption on brain reward response to UPF.

Aim 2: To determine the influence of chronic UPF consumption on ad libitum energy intake and food selection.

Aim 3: Explore the influence of UPF consumption on executive function, specifically inhibitory control, cognitive flexibility, working memory, and eating in the absence of hunger.

2.2 *State the hypotheses to be tested:*

We hypothesize blood oxygenation level dependent (BOLD) response in reward associated brain areas (ie. striatum and ventromedial prefrontal cortex) to UPF milkshake will be attenuated following the eucaloric UPF diet compared to the eucaloric MPF diet, and that changes will be associated with increased ad libitum energy intake at the breakfast buffet meal. We further hypothesize that when compared to a eucaloric MPF diet, a eucaloric UPF diet will increase energy intake at an ad libitum breakfast buffet meal and preference for UPF will be increased. We hypothesize that UPF exposure will be associated with reductions in executive function performance compared to MPF exposure, and that eating in the absence of hunger will increase with UPF exposure.

3.0 Background

3.1 *Summarize the relevant prior research on this topic and gaps in current knowledge within the field of study:*

Most individuals with obesity become so before age 35. In the US population, adolescents have the highest ultra- processed food consumption (68% of total energy) and the lowest diet quality. Given that ultra-processed foods represent two-thirds of the energy consumed by adolescents and young adults, research is needed to understand the influence of food processing on eating behaviors, particularly in the late adolescence and

early adulthood life stage. During this time, individuals have increasing independence in food choice and it represents a key developmental period for executive function, processes that affect life-long mental and physical health. Evidence from pre-clinical studies demonstrates rodents maintained on a “cafeteria diet” comprised of ultra-processed ingredients have greater energy intake, weight gain, and alterations in brain circuitry that regulates both energy intake and executive function than those exposed to a standard diet. However, the impact of ultra- processed foods on the brain circuits underlying reward processing, food intake regulation, food choice, and executive function in humans is unknown. Controlled diet interventions are needed to fill this void.

3.2 Describe any relevant preliminary data:

N/A

3.3 Based on the existing literature, provide the scientific or scholarly rationale for and significance of your research and how will it add to existing knowledge:

More than two-thirds of the energy consumed by US adolescents (67%) comes from UPF, and UPF consumption is increasing and UPF exposure is associated with increased ad libitum EI, weight gain and obesity. Furthermore, normal weight individuals aged 18-30 years are likely to become overweight or obese in their next two decades of life; and to date, no experimental studies have investigated the brain response to UPF, or the influence of UPF consumption on ad libitum EI and food selection in adolescents and emerging adults (age 18-25). We will overcome the following limitations of existing research. First, previous studies have not controlled for energy density, which is a major potential confounding factor. Second, the one existing experimental trial on UPF did not include brain imaging measures, or a washout phase, which is needed to address potential carryover effects of high and low UPF diets. Our findings will contribute importantly to an emerging neurobiological understanding of the adverse effects of UPF consumption and how this may contribute to energy overconsumption, weight gain, and obesity risk. This research could have important practice and policy implications. Dietary guidelines for obesity prevention devote minimal attention to processed foods, yet recommendations to limit UPF consumption may be warranted, particularly for adolescents and young adults.

4.0 Study Endpoints

*4.1 Describe the primary and secondary **study** endpoints. See links below for discussion of study endpoints and how they may differ from study objectives. These are most common in clinical trials but are sometimes*

applicable to other types of biomedical research, as well as social, behavioral, or educational research. See link below for a discussion.

https://docs.google.com/document/d/1Wocz7K7a0hCQJPPO_khh511SOQjhGDDGHzcOPRHR5Tw/edit?usp=sharing

Primary endpoint: Assess changes in reward response to UPF-rich milkshake via fMRI before and after each feeding period.

Secondary endpoint: Evaluate energy (kcal) intake and food choice when both UPF and MPF are available immediately following each feeding period.

Other endpoints: eating in the absence of hunger, executive function

4.2 *Describe any primary or secondary safety endpoints. These should be included for all studies that are greater than minimal risk. (Minimal risk: The probability and magnitude of harm or discomfort anticipated in the research that are not greater in and of themselves than those ordinarily encountered in daily life or during the performance of routine physical or psychological examinations or tests.):*

There are no safety endpoints

5.0 Study Design and Statistical Analysis Plan

5.1 *Describe the basic study design/approach (e.g., qualitative study using five focus groups of first year students to describe assimilation into the university community; randomized controlled trial of a behavioral change intervention to increase dietary intake of whole grains; pre- post-test evaluation of new pedagogical techniques to improve adult literacy):*

Individuals aged 18-25 years (n=32), will undergo two 14-day controlled feeding conditions in a randomly assigned order (crossover): un/minimally processed diet (0% UPF, “MPF”) or a diet containing 81% energy from UPF (“UPF”). Randomization sequence will be stratified based upon BMI status, sex, and age (18-21y, 22-25y). Diets will be eucaloric and matched for potential confounding factors including macronutrients, fiber, and energy density. A 4-week washout period will occur between dietary conditions. To assess changes in reward processing, brain response to a UPF-rich beverage (“milkshake”) will be assessed via fMRI before and after each feeding period. Executive function will also be assessed before and after each feeding period. Measurements immediately following each feeding period will include ad libitum EI and

food selection containing both UPF and MPF and eating in the absence of hunger post-meal.

5.2 Describe corresponding data analysis plan/approach (e.g., content analysis of focus group transcripts; descriptive analysis followed by linear regression modeling; nonparametric analysis of pre- and post-test measures):

Effects on study outcomes will be assessed using mixed effect linear models to estimate treatment differences between diet conditions. Exploratory path analysis with multiple mediators will be utilized to understand mechanisms of change, and estimate effect sizes. Covariates will be included to control for baseline group differences, if any. Standard preprocessing and statistical techniques for fMRI data to look for relationships between neural activity and physiological measures upon chronic exposure to UPF. Standard fMRI processing techniques will also be used to calculate subcutaneous, visceral, and liver fat percentages.

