Screening visit 2 ([name]-CHBR Suite; ~ 1 hour): The second laboratory screening visit will consist of a mock fMRI scan to improve data quality and ensure

participants are eligible and willing to complete the fMRI measurement. Participants will fill our clincard forms and receive clincard.

Baseline Measurement 1, Diet Period 1 (229 Wallace Hall; ~1-1.5 hours): If participants are eligible and willing they will come in and undergo measurement of body composition (BIA), hip and waist measurements, and executive function.

Baseline Measurement 2, diet Period 2 ([name]-Human Neuroimaging Lab; ~2 hours): The second baseline measurement will consist of participants undergoing fMRI tasks with a dairy based milkshake and an abdominal fMRI. Participants will also complete a computerized Delay Discounting measure. Participants will then be randomly assigned to their first diet condition.

Two-week diet period 1 (12 daily visits [Mon-Sat], 334 Wallace Hall; ~30 min/day, 6 hours total): Following the eligibility screening and baseline measurements, participants will come into the lab each morning in the fasted state, be weighed (to insure weight stability), eat their breakfast in the dining laboratory, and be provided with a cooler of remaining food for the day. On the first Saturday of diet, participants will receive the Actigraph and have them until Thursday, when they should return it.. During the second week of the diet, the following measurements will be made: On day 13, executive functioning, body composition (BIA), and waist and hip measurements will be assessed. On day 14, meal palatability will be assessed using the LHS after their supervised breakfast meal, then they will travel to Roanoke for fMRI measurements.

Optional component: Participants may provide a 24-hour urine sample during this diet period, if they are willing to do so.

Day 14 fMRI 1 ([name]-Human Neuroimaging Lab; ~3 hours): After meal palatability assessment, the participant will travel to Roanoke to undergo fMRI with a dairy based milkshake after diet period to assess changes in brain response after exposure to the diet condition. Abdominal fMRI will be repeated to assess changes in subcutaneous, visceral, and liver fat. Computerized delay discounting task will be repeated after the diet period to assess any changes in discount rate. fMRI assessments will be performed ~ 3 hours after the supervised breakfast meal.

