Ad libitum Buffet Meal: (334 Wallace Hall; ~ 1 hour): On day 15, the participant will rate internal state, engage in an ad libitum energy intake and food selection assessment. Visual Analog Scales (VAS) will be completed at time 0 (baseline) and time 30 (30 minutes after exposure to the buffet meal). Time spent eating will be covertly recorded (meal start/stop time). Kcal and grams of food consumed will be covertly recorded, to calculate meal eating rate (g/min, kcal/min). Foods selected will also be covertly recorded. Eating in the absence of hunger will be assessed immediately after the buffet meal. Four snacks items will be provided and participants will be asked to take a bite of each one and rate its palatability using the LHS, and then be left alone to eat the remainder of the snacks or look at the magazines while they wait for the next part of the study. Participants will be left to consume the snacks or relax for 15 minutes.

22-253 Influence of ultra-processed foods on reward processing and energy intake

Eating in the Absence of Hunger Measurement (Take Home): Participants will be given a box of snacks to assess eating in the absence of hunger outside the laboratory environment. Snack boxes will be returned to study staff the next morning. Staff will document the amount and type of snacks consumed.

4 week washout period: Participants will be asked to resume their usual diet. In the final week of the washout (week 4), assessments of dietary intake, PA, EF, and fMRI will be completed in two baseline visits for the second feeding period (listed below). These will serve as the baseline assessments for the second feeding period. For females, washout duration may be extended to 6 weeks if needed, in order to schedule EF, fMRI, and ad libitum buffet meal post- testing in the same menstrual cycle phase.

Baseline Measurement 1, Diet Period 2 (229 Wallace Hall; ~1-1.5 hours): Participants will undergo executive function, BIA with hip and waist measurements,

Baseline Measurement 2, diet Period 2 ([name]-Human Neuroimaging Lab; ~3 hours): The second baseline measurement will consist of participants undergoing fMRI tasks with a dairy based milkshake. Abdominal fMRI will be completed to assess changes in subcutaneous, visceral, and liver fat. Computerized delay discounting task will be completed.

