**Baseline 2 measures will be done during the final week of washout (week 4)-can extend washout for women if needed (begin diet in early follicular phase of menstrual cycle or anytime for women with IUDs).

***Baseline fMRIs will be done after the participants usual breakfast since they are not on the controlled diet for the baseline test.

Detailed description of measures:

Medical History: Subjects will be asked to complete a medical history form, which will be used to screen for health problems (heart disease, stroke, respiratory disease, endocrine or metabolic disease, hematological/oncological disease, medication usage, food allergies and aversions) that would preclude participation. Usual physical activity habits will also be reported.

24-hour dietary recall: Participants will be asked to describe all foods and beverages consumed in the previous 24 hours. NOTE: a birthdate is required by this software when dietary data are entered, in order to generate a table of the participant's reported intake compared to age- and sex-based Dietary Reference Intake recommended intake values.

Mock fMRI training: "mock" MRI training session will be completed in the CHBR during which subjects will learn to swallow small amounts of liquids while lying down (Note: most people have no difficulty learning to swallow small quantities of liquid while lying down). This training will be performed in an MRI simulator that is the same bore size and similar environment to the real scanner, but does not contain a magnetic field. Subjects who have difficulty with supine swallowing or who express discomfort in the simulated fMRI environment will not continue in the study. At this time they will also be trained on the use of the LHS. This involves rating imagined sensations on the scale.

Body Mass and Composition: Body weight will be measured on a digital scale accurate to +/-0.01 kg. Height will be measured with a stadiometer. Percent body fat and fat-free mass will be measured in all subjects using BIA. This is a non-invasive technique that uses a device similar to a scale. A weak electric current flows through the body from two points, and the rate at which the current travels through the body can be used to estimate lean and adipose tissue mass. The current is not detectable to the individual undergoing the procedure.

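### Section 5.2 should replace its conditional covariate rule with a fixed crossover model: diet, period and each period's own baseline

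*Combined protocol and SAP*

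**What the plan says.** Section 5.2 is the whole analysis plan. Outcomes are to be analysed by "mixed effect linear models to estimate treatment differences between diet conditions", and the only rule on covariates is "Covariates will be included to control for baseline group differences, if any". It gives no list of covariates, no criterion for a difference, no response variable and no period term, and no other section supplies them.

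The primary endpoint in 4.1 is "Assess changes in reward response to UPF-rich milkshake via fMRI before and after each feeding period". Sections 1.0, 5.1, 8.1 and 8.2 also speak of change. The hypothesis in 2.2 says the response "will be attenuated following the eucaloric UPF diet compared to the eucaloric MPF diet", and the same sentence goes on to refer to changes.

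The trial collects a baseline for each period. Section 8.2 says of the assessments in the last washout week: "These will serve as the baseline assessments for the second feeding period". Section 3.3 describes a washout as "needed to address potential carryover effects of high and low UPF diets", but 5.2 does not mention carryover. Buffet intake, food selection and eating in the absence of hunger are measured only after each diet.

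**The concern.** Every participant receives both diets, so the only between-person groups are the two diet sequences. Sex, BMI and age are the same in both periods and drop out of the within-person diet difference when both periods are complete. Adding them because the groups look different therefore does almost nothing for the diet contrast. The covariate that can sharpen that contrast is the baseline taken before each diet, and 5.2 does not use it.

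Two things are at stake in a primary analysis of 26 completers. The first is precision that the existing data could supply. The second is freedom of choice: a covariate set settled after baseline data are seen, with no stated outcome form and no stated period term, leaves several primary models available.

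**Working it through.** **The plan's own figures.** Section 14.1 gives 26 completers for the primary aim and 20% attrition: 26/(1 − 0.20) = 32.5, rounded up to 33, which reproduces the recruitment figure. (The same section also gives 32; that is a separate matter.) The 26 cannot be reproduced, because no effect size, alpha or power is stated. With assumed two-sided 5% and 80% power, a paired t-test with n = 26 corresponds to a standardised effect of 0.572.

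**Variance of the three contrasts.** For each participant let B be the baseline difference and D the post-diet difference (UPF period minus MPF period), with equal variances set to 1 and correlation r. The documents do not give r, so a range is shown.

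- Change: Var(D − B) = 2(1 − r)
- Post-only: Var(D) = 1
- Baseline-adjusted: Var(D given B) = 1 − r²
- Change relative to adjusted: 2(1 − r)/(1 − r²) = 2/(1 + r)

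**Power at n = 26 if the trial was sized on change.** The adjusted analysis has standardised effect 0.572 × √(2/(1 + r)). The simulation used 40,000 trials per case, 13 per sequence, with period in every model, and so includes the degrees-of-freedom cost.

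| r | 2/(1 + r) | Adjusted, formula | Adjusted, simulated | Change |
|---|---|---|---|---|
| 0 | 2.00 | 98% | 97% | 80% |
| 0.33 | 1.50 | 93% | 92% | 80% |
| 0.57 | 1.27 | 89% | 87% | 80% |
| 0.9 | 1.05 | 82% | 80% | 80% |

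**Open choice.** With no diet effect, reporting whichever of change, post-only and adjusted gives the smallest p-value yields type I error of about 9 to 10% instead of 5%. If only a subset of these is really in play, the figure cannot be larger.

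**Conditional rule alone.** A fixed pre-test rule (adjust only if baselines differ at p < 0.05) gave simulated type I error of 3.8% to 5.0%. The rule alone does not inflate error.

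**Period term omitted.** Assume a period effect of 0.5 SD of the paired contrast and n = 26. If n1 and n2 participants complete the two sequences, the bias is (n1 − n2)/26 of the period effect, and the unmodelled period effect also inflates the residual variance.

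| Split | Bias, share of period effect | Type I error |
|---|---|---|
| 13/13 | 0 | 0.029 |
| 15/11 | 4/26 = 15.4% | 0.041 |
| 16/10 | 6/26 = 23.1% | 0.057 |
| 17/9 | 8/26 = 30.8% | 0.079 |

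Repeat simulations move the last two by about 0.002. At 13/13, power is 73% instead of 80%. For change scores this concerns only a difference between periods in within-period change, since a shift common to both scans of a period cancels.

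**Carryover.** Suppose a share c of the first diet's effect persists into period 2. If it persists in both period-2 scans, the means of D and B are both lowered by c/2 of the diet effect. The bias is then 0 for change and −(c/2)(1 − r) for adjusted. If it persists in the baseline only, the bias is +c/2 for change and +(c/2)r for adjusted. With c = 0.2 as an assumption:

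| r | Both scans: change | Both scans: adjusted | Baseline only: change | Baseline only: adjusted |
|---|---|---|---|---|
| 0 | 0 | −10% | +10% | 0 |
| 0.33 | 0 | −7% | +10% | +3% |
| 0.57 | 0 | −4% | +10% | +6% |
| 0.9 | 0 | −1% | +10% | +9% |

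**The case against.** The strongest reply is that the outcome is not really open. The documents name change throughout, and a mixed model of change with diet and period would close the gap while keeping the 4.1 endpoint. That model holds its assumed 80% power at every r, and it is unbiased when carryover is equal in both period-2 scans, where the adjusted contrast is not. This largely stands. It is why the change contrast should be reported beside the adjusted one, and why the case for adjustment is a gain in power and not the rescue of a failing design.

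A reader might infer from 2.2 that a post-only comparison is equally open and that power could collapse if r is high. The documents do not support that. The 2.2 sentence itself continues with changes, and the other sections agree.

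A reader might also infer that 5.2 was drafted for a parallel-group trial. The word group could equally mean the two sequences. On either reading the rule depends on the data and gives the diet contrast little. The sentence also directly follows the one on path analysis and may be meant to govern that analysis too, so simply deleting it could remove something intended.

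Finally, r is unknown. "Baseline fMRIs will be done after the participants usual breakfast", while post-diet scans come about 3 "hours after the supervised breakfast meal". That might lower r, but a usual breakfast that is the same at both baselines cancels from the between-period difference. No figure can be put on it.

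**Conclusion.** The point holds as a defect of specification with a concrete better method, and it should be corrected before analysis. Section 5.2 leaves the covariates to the data, does not carry the change outcome into the model, omits period, and leaves the period baselines unused.

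The size depends on r. Adjustment adds about 17 points of power over change at r = 0, 12 at 0.33, 7 at 0.57 and essentially none at 0.9, given the assumed alpha, power and equal variances.

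Two stronger claims should not be drawn. First, the conditional covariate rule has not been shown to inflate type I error by itself; the 9 to 10% comes from choosing freely among three outcome forms. Second, leaving out period is neither always harmless nor always harmful. With the assumed 0.5 SD effect the test is conservative near balance and anti-conservative at 16/10 or worse. The documents describe stratified randomisation but no blocking, so the likely split among completers cannot be fixed from them.

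**What to change.** For the diet-effect models, replace the conditional sentence in 5.2 with fixed specifications.

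- **Outcomes with a baseline in each period** (scalar fMRI response per region, executive function, delay discounting, body composition, abdominal fat): a mixed model of the post-diet value with diet and period as fixed effects, the within-person deviation of the period baseline as covariate, and a random participant effect. The participant's mean baseline may be added; with complete balanced data it leaves the diet contrast unchanged.
- **Alongside it:** the unadjusted change contrast with diet and period. State that the two differ in bias if the first diet carries over into the washout-week-4 baseline or into period 2.
- **Buffet intake, food selection and eating in the absence of hunger:** diet and period as fixed effects with a random participant effect, since no period baseline exists.
- **Path analysis:** state separately which covariates, if any, it uses.

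The cost is one or two degrees of freedom, at most about 2 points of power at n = 26, and no new data. One task comes first: a scalar response must be defined for each region named in 2.2 (striatum and ventromedial prefrontal cortex), because the documents do not define one.
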